Confidentiality Statement: The information contained within this document is not to be disclosed in any way without the prior permission of the Protocol Chair, or the Division of Allergy, Immunology and Transplantation, National Institute of Allergy and Infectious Diseases of the National Institutes of Health.

Protocol Synopsis

Title	T Cell Reagent Research for Monitoring T Cells in Food Allergy Phase 2 study using Food Allergen Oral Immunotherapy for Shrimp or Cashew Allergies
Short Title	Monitoring T cells in Food Allergy (MOTIF)
Clinical Phase	Phase II
Number of Sites	1
IND Sponsor/Number	[name] [REDACTED]
Study Objectives	
Primary Objective:
 
To determine T cell, immune-based mechanisms of food allergy (FA) and to optimize T cell reagent discovery and validation by obtaining blood samples from FA participants undergoing oral immunotherapy (OIT), and simultaneously, develop diagnostic, prognostic, and mechanistic tools based on the T cell reagents developed during the course of OIT.
 
Secondary Objectives:
 
 • Identify, characterize, and validate new T cell epitopes for important food allergens (cashew, shrimp) • Track the numbers and functions of epitope-specific T cells during stages of FA OIT • Associate these parameters with phenotype and endotype characterizations in food-allergic individuals • Determine whether immune monitoring measurements reflecting these underlying mechanisms can be used to predict responses to OIT 
Exploratory Clinical objectives:
 
 • To evaluate desensitization protocols for cashew and shrimp in allergic individuals 
Determine whether the achievement of sustained unresponsiveness is different between cashew, or shrimp food allergy participants after a period of withdrawal from OIT

Study Design	A prospective Phase 2, single-center, single-allergen OIT of cashew or shrimp in participants with proven allergies to either cashew or shrimp, respectively. We intend to treat 72 participants, ages 7 to 55 years with an allergy to either cashew, or shrimp determined by Double Blind-Placebo Controlled-Food Challenges (DBPCFC), allergy history, clinical symptoms, food-allergen (FA)-specific IgE levels, and skin prick test (SPT). Enrolled participants must be

	
positive at or before the 300 mg (443 mg cumulative) dosing level of FA protein. OIT treatment groups will be cashew or shrimp.
 
All cohorts will undergo an updosing regimen starting at 5 mg allergen, with dose escalation every 2 weeks to reach a 1,000 mg dose at week 28, after which they will be maintained at that dose for 24 weeks. At the conclusion of the maintenance phase (Week 52), participants will undergo DBPCFC. Participants that pass their food challenge with no or mild objective reactions to up to a cumulative 2043 mg of the FA allergen in their OIT at the end of this phase (primary outcome) will be considered desensitized and have successfully met the primary endpoint.
 
All participants then will continue in the study by undergoing a withdrawal from OIT for 6 weeks to examine mechanisms underlying sustained responsiveness (SU) which will be defined as a participant’s passing DBPCFC with no or mild objective reaction to up to a cumulative 2043 mg of the FA allergen in their DBPCFC at week 58. Those participants who pass the Week 58 challenge up to a cumulative of 2043 mg will be given the option to continue the withdrawal phase up to Week 64 which will be end of study. Week 58 will be end of study for those who do not opt for this continuation of withdrawal.

Primary Endpoint(s)
	
Change in expression of CD28 in the CD4+ allergen specific (CD154+) T-cells at 52 weeks relative to baseline values between those who do and do not tolerate a cumulative of 2043 mg in the DBPCFC at week 52.

Secondary Endpoint(s)
	
 • Compare changes in expression of CD28+ allergen specific (CD154+) T-cells over multiple time points from baseline to week 58 and week 64 between those with sustained unresponsiveness (SU) vs those desensitized but SU failures vs those who did not pass the desensitization DBPCFC • Compare changes in the following measures in CD4+CD28+ allergen specific (CD154+) T-cells at week 52 and week 58 between those who achieved sustained unresponsiveness (SU) vs those desensitized but SU failures vs those who did not pass the desensitization DBPCFC at week 52. 
 ○ Levels of IFN-gamma ○ Levels of IL-4 ○ Receptor diversity in allergen specific T cell CDR3b as compared to non-specific T cells ○ Levels of IL-10 ○ Levels of TGF beta ○ Levels of GPR15 ○ Levels of CCR4+ ○ Levels of CRTh2

Exploratory Clinical Objectives	
Comparing the proportion of participants who become desensitized vs all others (i.e. treatment failures) at week 52 DBPCFC.
 
Comparing the proportion of participants who reach SU vs desensitized but SU failures at week 58 DBPCFC.
 
Comparing changes in the transcriptomes and phenotypes of tetramer+ T cells from baseline to 52 weeks, 58 weeks, and to 64 weeks.

Safety Endpoints	
The proportion of participants with only mild AEs during the course of the study.
 
The proportion of participants with respiratory or abdominal severe AEs during the course of the study.
 
The proportion of participants who successfully pass a DBPCFC with no or mild objective reactions to a cumulative 2043 mg of the FA allergen at the end of OIT (desensitization, week 52).
 
The proportion of participants who successfully pass a DBPCFC with no or mild objective reactions to a cumulative 2043 mg of the FA allergen after 6 weeks off OIT (sustained unresponsiveness, week 58) and the subsequent optional DBPCFC at Week 64 (please see Appendix 2).

Accrual Objective	72
Study Duration	Participants will be in an active phase of the protocol for about 16 months (see Appendix 1 for individual subject timeline)
Treatment Description	
Subjects will undergo an initial dose day for consumption of a maximum single dose of 5 mg food allergen (cashew, or shrimp) protein. They will consume this dose at home for two weeks and document reactions. Upon returning to the SNP-CRU (Sean N Parker-Clinical Research Unit) two weeks later, a dose escalation will be attempted. This escalation will continue until the subject reaches a maximum dose of 1,000 mg protein daily at week 28. Participants then will continue that maintenance dose until Week 52 from baseline before they undergo DBPCFC, which will mark the end of treatment intervention.

Inclusion Criteria	
 • Subject and/or parent guardian must be able to understand and provide informed consent • Age 7 through 55 years (inclusive) • Clinical history of allergy to cashew or shrimp-containing foods

	
 • Serum IgE to cashew or shrimp of ≥ 0.35 kUA/L [determined by UniCAP™ within the past 12 months] and/or a SPT to cashew or shrimp ≥ 3 mm compared to control • Experience dose-limiting symptoms at or before the 300 mg challenge dose of FA protein on Screening DBPCFC conducted in accordance with PRACTALL guidelines • Written informed consent from adult participants • Written informed consent from parent/guardian for minor participants • Written assent from minor participants as appropriate (e.g., above the age of 7 years or the applicable age per local regulatory requirements) • All female subjects of child-bearing potential will be required to provide a blood or urine sample for pregnancy testing that must be negative one week before being allowed to participate in the study. • Use of effective birth control by female participants of child-bearing potential

Exclusion Criteria
	
 • Inability or unwillingness of a participant to give written informed consent or comply with study protocol • History of uncontrolled cardiovascular disease, including uncontrolled hypertension • History of other chronic disease (other than asthma, atopic dermatitis, or allergic rhinitis) requiring therapy (e.g., heart disease, diabetes) that is, or is at significant risk of becoming unstable or requiring a change in chronic therapeutic regimen and, in the opinion of the Principal Investigator, would represent a risk to the subject’s health or safety in this study or the subject’s ability to comply with the study protocol. • History of eosinophilic esophagitis (EoE), other eosinophilic gastrointestinal disease, chronic, recurrent, or severe gastroesophageal reflux disease (GERD) grade 3 according to CTCAE version 5.0, symptoms of dysphagia (e.g., difficulty swallowing, food “getting stuck”), or recurrent gastrointestinal symptoms of undiagnosed etiology • Current participation in any other interventional study • Subject is currently in the build-up phase of immunotherapy to another allergen and is on maintenance immunotherapy dose for any allergen related to cashew or shrimp • Severe asthma (NAEPP EPR-3 Medication Criteria Steps 5 or 6) • Mild or moderate asthma (NAEPP EPR-3 Medication Criteria Steps 1-4), if not controlled as indicated by an $ACT \leq 19$ • A hospitalization for asthma in the past 6 months • ER visit for asthma within the past 6 months • Burst or steroid course for asthma in the past 6 months • Use of omalizumab or biologic therapy (e.g., infliximab, rituximab, etc.) within the past 6 months • Use of complementary and alternative medicine (CAM) treatment modalities (e.g., herbal remedies) for atopic and /or

	
non-atopic disease within 90 days preceding Initial Dose Escalation Day (IDED) or at any time after the IDED
 
 • Use of beta-blockers (oral) • Pregnancy or lactation • Allergy to oat • History of severe anaphylaxis to cashew or shrimp with symptoms including hypotension requiring fluid resuscitation and/or the need for mechanical ventilation within the last year • Use of investigational drugs within 12 weeks of participation • Past or current medical problems or findings from physical assessment or laboratory testing that are not listed above, which, in the opinion of the investigator, may pose additional risks from participation in the study, may interfere with the participant’s ability to comply with study requirements or that may impact the quality or interpretation of the data obtained from the study

Study Stopping Rules
	
During the study, if the investigator or the NIAID Medical Officer discovers conditions that indicate that the study should be discontinued, an appropriate procedure for stopping the study pending DSMB review will be instituted.
 
If any of the stopping rules listed below are met, study enrollment will be suspended, the Initial dose day will be suspended, dose escalation during Build-up will be stopped, and all enrolled participants will remain on their current dose pending expedited review of all pertinent data by the Data Safety Monitoring Board:
 
 • Any death related to cashew or shrimp OIT dosing • More than 3 cases of CoFAR Grade 4 AE related to food allergen dosing or to oral food challenge. • More than 3 participants require more than 2 injections of epinephrine during a single dosing of cashew or shrimp OIT investigational product • More than 3 of the following events: 
 ○ Severe adverse event, other than anaphylaxis, related to investigational product ○ Eosinophilic esophagitis

Participant Stopping Rules
	
 1. The participant elects to withdraw consent from all future study activities, including follow-up. 2. The participant is “lost to follow-up” (i.e., no further follow-up is possible because attempts to reestablish contact with the participant have failed). 3. The participant dies. 4. The Investigator no longer believes participation is in the best interest of the participant. 5. Individual safety stopping rules: 
 a. Anaphylaxis resulting in hypotension, neurological compromise or mechanical ventilation secondary to OIT dosing or food challenge

	
 b. Any subject deemed to have severe allergic reactions and who receives aggressive therapy (e.g., hypotension with IV fluid resuscitation, mechanical ventilation, more than 2 doses of epinephrine for a life-threatening reaction) at any time should be discontinued from further therapy c. Other circumstances including, but not limited to, the following: 
 ○ Severe adverse event, other than anaphylaxis, related to investigational product ○ Pregnancy

Premature Discontinuation of Investigational Agent
	
 • Poor control or persistent activation of secondary atopic disease (e.g., AD, asthma), at the discretion of the investigator • Started on beta-blockers, or other prohibited medications, with no alternative medications available per the prescribing physician • Non-adherence with home OIT dosing protocol (excessive missed days more than 20 days) without consulting with study staff would be a safety issue warranting discontinuation • The subject develops biopsy-documented eosinophilic esophagitis (EoE) with synchronous clinical symptoms or other eosinophilic gastrointestinal disease 
Study therapy may also be prematurely discontinued for any participant if the investigator believes that the study treatment is no longer in the best interest of the participant.

Table of Contents

Study Definitions Page	14
1. Background and Rationale	16
1.1. Background and Scientific Rationale.....	16
1.2. Rationale for Selection of Investigational Product or Intervention.....	16
1.3. Preclinical Experience	16
1.4. Clinical Studies	17
2. Study Hypotheses/Objectives.....	17
2.1. Primary Objective(s).....	18
2.2. Secondary Objective(s)	18
2.3. Exploratory Clinical objectives:	18
2.4. Safety Objectives.....	18

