3.5. Safety Endpoints

- The proportion of participants with only mild AEs (i.e. Grade 1) during the course of the study.
- The proportion of participants with respiratory or abdominal severe AEs (i.e. Grade 3) during the course of the study.
- The proportion of participants who successfully pass a DBPCFC with no or mild objective reactions to a cumulative 2043 mg of the FA allergen at the end of OIT (desensitization, week 52).
- The proportion of participants who successfully pass a DBPCFC with no or mild objective reactions to a cumulative 2043 mg of the FA allergen after 6 weeks off OIT (sustained unresponsiveness, week 58) and subsequent optional DBPCFC at week 64 (please see Appendix 2).

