2. Two or more of the following that occur rapidly after exposure to a likely allergen for that patient (minutes to several hours):
 - a. Involvement of the skin-mucosal tissue (eg, generalized hives, itch-flush, swollen lips-tongue-uvula)
 - b. Respiratory compromise (eg, dyspnea, wheeze-bronchospasm, stridor, reduced PEF, hypoxemia)
 - c. Reduced BP or associated symptoms (eg, hypotonia [collapse], syncope, incontinence)
 - d. Persistent gastrointestinal symptoms (eg, crampy abdominal pain, vomiting)
3. Reduced BP after exposure to known allergen for that patient (minutes to several hours):
 - a. Infants and children: low systolic BP* (age specific) or greater than 30% decrease in systolic BP
 - b. Adults: systolic BP of less than 90 mm Hg or greater than 30% decrease from that person's baseline

*Low Systolic BP is defined as less than $(70 + [2 \times \text{age}])$ mm Hg

Anaphylaxis severity will be graded according to the following CoFAR specific grading system scale:

Anaphylaxis Staging System

Staging System of Severity of Anaphylaxis	
Stage	Defined By
1. Mild (skin & subcutaneous tissues, GI, &/or mild respiratory)	Flushing, urticaria, periorbital or facial angioedema; mild dyspnea, wheeze or upper respiratory symptoms; mild abdominal pain and/or emesis
2. Moderate (mild symptoms + features suggesting moderate respiratory, cardiovascular or GI symptoms)	Marked dysphagia, hoarseness and/or stridor; shortness of breath, wheezing & retractions; crampy abdominal pain, recurrent vomiting and/or diarrhea; and/or mild dizziness
3. Severe (hypoxia, hypotension*, or neurological compromise)	Cyanosis or $\text{SpO}_2 \leq 92\%$ at any stage, hypotension, confusion, collapse, loss of consciousness; or incontinence

* https://ctep.cancer.gov/protocoldevelopment/electronic_applications/docs/CTCAE_v5_Quick_Reference_5x7.pdf

Other allergic reactions will be graded according to the following CoFAR specific grading system:

Table 4 COFAR Grading Scale for Systemic Allergic Reactions

Grade 1	Grade 2	Grade 3	Grade 4	Grade 5
---------	---------	---------	---------	---------

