Appendix 2: Participant Disposition

If pregnancy or if hypotensive event related to study drug occurs, participants will be terminated from the study

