Appendix 3: Dose Limiting Symptoms (CoFAR guidelines)

Challenges will be considered positive with the occurrence of any dose-limiting symptoms, which in the view of the PI indicate a true allergic reaction which should preclude the administration of any further doses.

During a dose escalation in clinic, the clinician will use the following criteria to determine if the dose was well tolerated and if the participant may go home on that dose.

As defined below, mild symptoms are not usually considered dose-limiting, although a combination of mild symptoms might lead to the cessation of a challenge or reduction in the dose that the participant is allowed to go home on at the discretion of the PI

All moderate and severe symptoms as defined below are considered dose-limiting.

Mild:

- Skin – limited (few) or localized hives, swelling (e.g., mild lip edema), skin flushing (e.g., few areas of faint erythema) or mild pruritus (e.g., occasional scratching)
- Respiratory – rhinorrhea (e.g., occasional sniffing or sneezing), nasal congestion, occasional cough, throat discomfort
- GI – mild abdominal discomfort (including mild nausea with or without decreased activity), isolated emesis thought to be secondary to gag

Moderate:

- Skin – systemic hives (e.g., numerous or widespread hives), swelling (e.g., significant lip or face edema), pruritus causing protracted scratching, more than a few areas of erythema or pronounced erythema
- Respiratory – throat tightness without hoarseness, persistent cough, wheezing without dyspnea

- GI – persistent moderate abdominal pain/cramping/nausea with decreased activity, vomiting

Severe:

- Skin – severe generalized urticaria/angioedema/erythema
- Respiratory – laryngeal edema, throat tightness with hoarseness, wheezing with dyspnea, stridor
- GI – severe abdominal pain/cramping/repetitive vomiting
- Neurological – change in mental status
- Circulatory – clinically significant hypotension

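### The severe-AE safety endpoint counts only respiratory or abdominal events, and in Section 3.5 only Grade 3, so isolated hypotension, neurological compromise and Grade 4 reactions can fall outside it

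*Combined protocol and SAP*

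**What the plan says.** The synopsis gives the endpoint as "The proportion of participants with respiratory or abdominal severe AEs during the course of the study". Sections 2.4 and 13.2.2 carry the same definition. Section 3.5 adds a grade: "The proportion of participants with respiratory or abdominal severe AEs (i.e. Grade 3) during the course of the study".

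Three scales in the protocol describe severity of an allergic reaction:

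- Appendix 3 (dose-limiting symptoms) has severe entries for five systems. Besides respiratory and GI, these are "Skin – severe generalized urticaria/angioedema/erythema", "Neurological – change in mental status" and "Circulatory – clinically significant hypotension".
- The anaphylaxis staging in Section 12.3.1 defines its top stage as "Severe (hypoxia, hypotension*, or neurological compromise".
- Table 4 in Section 12.3.1 (CoFAR grading) limits Grade 3 to lower respiratory and GI reactions. Laryngeal edema, hypoxia, refractory or mechanically supported respiratory reactions, and reduced blood pressure with end-organ dysfunction are in Grade 4.

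Non-allergic events are graded by CTCAE, where Section 12.3.1 labels Grade 3 severe and Grade 4 life-threatening or disabling.

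On consequences, Appendix 2 says that "if hypotensive event related to study drug occurs, participants will be terminated from the study". Synopsis participant stopping rule 5a covers anaphylaxis with hypotension or neurological compromise, and Section 12.8.2.2 makes more than 2 hypotension cases a trigger for DSMB review.

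Section 13.2.2 alone also lists the frequencies of anaphylaxis, of rescue epinephrine use and of AEs that lead to early withdrawal.

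**The concern.** The endpoint is narrower than the protocol's own account of a severe reaction, and the events it leaves out include some that the protocol treats as gravest. A participant whose only severe reaction is hypotension or altered mental status is not in the severe-AE proportion. That participant is not in the only-mild-AEs proportion either, and so falls between the two AE proportions. In Section 3.5 the same can happen, because of grade, to a participant whose worst event is Grade 4 laryngeal edema or hypoxia.

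At stake is a safety proportion that can only understate the share of participants with a severe reaction, in a trial that names safety as one of its purposes (Section 3.1). The documents give no reason for the restriction.

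**Working it through.** The plan states no figure for this endpoint, so there is nothing to reproduce. The check sets the definition against the scales, then looks at how sensitive a sparse count is.

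**Step 1. Which isolated reactions are counted?**

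| Isolated reaction | Appendix 3 | Anaphylaxis staging | Table 4 | Synopsis, 2.4, 13.2.2 | Section 3.5 (Grade 3) |
|---|---|---|---|---|---|
| Lower respiratory or severe GI, Grade 3 | Severe entries in both systems | Not the criterion for the top stage | Grade 3 | Counted | Counted |
| Laryngeal edema | Severe | Not named | Grade 4 | Counted if severe includes Grade 4; not stated | Not counted, by grade |
| Hypoxia | Not named | Severe | Grade 4 | Counted if severe includes Grade 4; not stated | Not counted, by grade |
| Hypotension | Severe if clinically significant | Severe | Grade 4 if with end-organ dysfunction | Not counted, by system | Not counted, by system; Grade 4 cases also by grade |
| Change in mental status | Severe | Severe | No separate entry | Not counted, by system | Not counted, by system |
| Severe generalized skin reaction | Severe | Skin is in stage 1 | Urticaria and angioedema only in Grades 1 and 2 | Not counted, by system | Not counted, by system |

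Hypotension is outside all four wordings. The skin row is an omission of a severe event only on the Appendix 3 scale. Section 3.5 has a second gap, by grade, within the respiratory system itself. Non-allergic CTCAE events of Grade 3 or higher in other organ systems are also outside all four wordings.

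**Step 2. Do the other measures in Section 13.2.2 catch them?**

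- Anaphylaxis frequency: under the third criterion in Section 12.3.1, reduced blood pressure after a known allergen is anaphylaxis on its own, so hypotension is caught. An isolated skin reaction meets none of the three criteria. No tabulation by stage is promised.
- AEs leading to early withdrawal: drug-related hypotension ends participation under Appendix 2, so it is caught, pooled with all other causes.
- Neither is stated as a proportion of participants with a severe reaction. Neither appears in the synopsis, Section 2.4 or Section 3.5.

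**Step 3. How much can one event matter?**

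Inputs: n = 72 (Section 3.1); fewer than 1% of subjects expected to have severe symptoms (Section 5.2, risks in the medical literature).

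- Expected participants at 1%: 72 × 0.01 = 0.72. At 0.5%: 72 × 0.005 = 0.36.
- P(at least one) = 1 − (1 − p)^72: 1 − 0.99^72 = 0.515 at 1%; 1 − 0.995^72 = 0.303 at 0.5%.
- One participant is 1/72 = 1.4%. Omitting a sole event moves the result from 1.4% to 0%.
- With 0 of 72 recorded, the one-sided 95% upper bound is 1 − 0.05^(1/72) = 4.1%.

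The share s of participants with severe reactions whom the endpoint would miss is not in the documents. As an assumption, take a total rate of 1% and s from 10% to 50%. The chance that the endpoint records anyone is then 1 − (1 − 0.01(1 − s))^72:

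| Assumed s | Rate still counted | P(at least one counted) |
|---|---|---|
| 0 | 1.0% | 0.515 |
| 10% | 0.9% | 0.478 |
| 25% | 0.75% | 0.418 |
| 50% | 0.5% | 0.303 |

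**The case against.** The strongest defence is that the wording follows the grading scale. Section 12.3.1 assigns Table 4 to allergic reactions other than anaphylaxis, and its Grade 3 consists only of lower respiratory and GI reactions. Appendix 3 is written as dose-limiting criteria for challenges and in-clinic escalation. On this view Section 3.5 closely restates CoFAR Grade 3 and makes no selective choice of systems. That stands as an explanation of where the wording may come from. It also disposes of a tempting summary, that two of five severe systems are counted and grade is irrelevant: the five systems are Appendix 3's, and Section 3.5 names a grade. It does not close the gap, because the same table puts hypotension with end-organ dysfunction in Grade 4, above the level the endpoint names.

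The second defence is that nothing is lost: AEs are recorded, hypotension and Grade 4 events have DSMB review or study stopping triggers, and Section 13.2.2 lists anaphylaxis and withdrawal AEs. This stands in large part. A reader might infer that hypotension disappears from the safety results; the documents do not support that. What remains is that no listed measure gives the proportion of participants with a severe reaction.

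The third is that the line states its own limit. A reader might infer that the trial could report no severe AEs after stopping participants for hypotension. As written, it would report no respiratory or abdominal severe AEs, and nothing in the documents makes it the headline safety result. This stands; the risk is of misreading.

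Finally, any single event in 72 is 1.4%, whatever its organ system, and the below-1% figure is a general expectation for oral immunotherapy, not split by system. This stands too. The arithmetic shows how sparse the counts are; it does not estimate the bias.

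**Conclusion.** The concern holds as a gap in an endpoint definition. All four wordings omit isolated hypotension and neurological compromise, and Section 3.5, read literally, also omits Grade 4 respiratory reactions. The omission of severe skin reactions depends on using Appendix 3.

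The direction is one-sided, since the omission can only lower the proportion. Its size cannot be given, because the documents do not state how many severe events would be isolated and outside the counted systems or grade. At 72 participants and an expected rate below 1%, a single omitted participant is enough to change 1.4% to zero. A participant with hypotension who also has a severe respiratory or abdominal reaction that falls within the named grade would still be counted.

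The CD28 primary analysis is not affected. The definition should be corrected before the safety results are tabulated.

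**What to change.** In the synopsis and Sections 2.4, 3.5 and 13.2.2, define the endpoint as the proportion of participants with any AE of Grade 3 or higher in any organ system, using Table 4 for allergic reactions and CTCAE for other AEs, and including severe-stage anaphylaxis. Naming Grade 3 or higher is essential: wording that says only any severe AE could still exclude Grade 4 events, given the labels in Sections 3.5 and 12.3.1. Including severe-stage anaphylaxis brings in neurological compromise staged as anaphylaxis, for which Table 4 has no separate entry.

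Report sub-rows for respiratory/abdominal, circulatory, neurological and skin, so that the present figure stays visible.

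For this endpoint, state how Appendix 3, the anaphylaxis staging and Table 4 map to one another, including where a change in mental status without anaphylaxis and a severe generalized skin reaction belong. This concerns reporting only and calls for no change to stopping or management rules.

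The cost is wording in four places and a short mapping. AEs of every grade are already recorded, and CoFAR grading already requires the organ system to be assessed. The reported severe rate may be slightly less favourable.
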